3.4.3. Plasma PK Parameters of [¹⁴C]PF-07220060

For **Cohort 2**, following a single IV microtracer dose of [¹⁴C]PF-07220060 at 2 hours post oral dose, IV plasma PK parameters of [¹⁴C]PF-07220060 will be derived from plasma radioactivity concentration equivalent-time profiles following chromatographic separation of [¹⁴C]PF-07220060 (ie. HPLC-AMS analysis).

Actual administered [¹⁴C] doses will be used for the [¹⁴C]PF-07220060 PK parameter calculations.

The plasma PK parameters will be derived (as data permits) from the concentration-time data using standard noncompartmental methods as outlined in [Table 2](#). Actual PK sampling times will be used in the derivation of PK parameters. In the case that actual PK sampling times are not available, nominal PK sampling time will be used in the derivation of PK parameters.

3.4.4. Urine PK Parameters of PF-07220060

The following urine PK parameters will be calculated using the outlined methods in [Table 3](#).

Table 3 Urine PK Parameters Definitions

Parameter	Definition	Method of Determination
Total ¹⁴C_Urine_PO	Total cumulative radioactivity excreted into urine from time 0 to the time of last measurable concentration following oral administration of [¹⁴C]PF-07220060 (Cohort 1 only)	Directly from observed [¹⁴C] data
Total ¹⁴C_Urine_IV	Total cumulative radioactivity excreted into urine from time 0 to the time of last measurable concentration following intravenously administered [¹⁴C]PF-07220060 microtracer dose (Cohort 2 only)	Directly from observed [¹⁴C] data
% ¹⁴C_Urine_PO	% of radioactivity in the urine following oral administration expressed as a percent of the radioactive dose administered (Cohort 1 only)	(Total ¹⁴C_Urine_PO/[¹⁴C] Dose_{po}) *100 where, [¹⁴C] Dose_{po} is orally administered dose of [¹⁴C]PF-07220060
% ¹⁴C_Urine_IV	% of radioactivity in the urine following IV administration expressed as a percent of the radioactive dose administered (Cohort 2 only)	(Total ¹⁴C_Urine_IV/[¹⁴C] Dose_{iv}) *100 where, [¹⁴C] Dose_{iv} is [¹⁴C] intravenously administered dose of [¹⁴C]PF-07220060
F_a	Fraction Absorbed	[Total ¹⁴C_Urine_PO/Total ¹⁴C_Urine_IV]*[¹⁴Cdose_{iv}/¹⁴Cdose_{po}]
Ae (PF-07220060 PO in Cohort 1)	Amount of unchanged drug excreted in urine	Sum of [PF-07220060 urine concentration* sample volume] for each collection interval
Ae% (PF-07220060 PO in Cohort 1)	Percent of dose recovered unchanged in urine	Ae/Dose*100
CL_r (PF-07220060 PO in Cohort 1)	Renal clearance (oral)	Aet/AUC_t where Aet is the amount of unchanged drug excreted in urine from 0 time until time t following oral dose of PF-07220060

3.4.5. Plasma PK Parameters of Total Radioactivity [¹⁴C]

For **Cohort 1**, following a single oral administration of a microtracer dose of [¹⁴C]PF-07220060, oral PK parameters for total [¹⁴C] radioactivity will be derived from the concentration equivalent-time profiles, where appropriate. PK parameters for total radioactivity [¹⁴C] will be computed based on AMS analysis.

For **Cohort 2**, following a single oral administration of PF-07220060 followed by administration of a single IV dose of [¹⁴C]PF-07220060, PK parameters for total [¹⁴C] radioactivity will be derived from the concentration equivalent-time profiles, where

appropriate. PK parameters for total radioactivity [^{14}C] will be computed based on AMS analysis.

Actual administered [^{14}C] doses will be used for the total [^{14}C] PK parameter calculations.

The plasma PK parameters will be derived (as data permits) from the concentration-time data using standard noncompartmental methods as outlined in Table 2. Actual PK sampling times will be used in the derivation of PK parameters. In the case that actual PK sampling times are not available, nominal PK sampling time will be used in the derivation of PK parameters.

3.4.6. Allelic Variants of Drug Metabolizing Enzymes and Transporters

A 4-mL blood PGx sample for DNA isolation will be collected into plastic K₂EDTA tubes, as defined in the SoA given in the protocol. The DNA sample will be analyzed for the purpose of assessing the impact of allelic variants of genes encoding drug metabolizing enzymes and transporters including, but not limited to, CYP3A and UGT2B7 on the ADME of the PF-07220060.

3.4.7. Taste Assessment Data

The data collected for taste assessment using the sponsor-provided taste questionnaire will be numerically derived by measuring the length (using a scale with gradation of at least 0.1 centimeter) of the “x” marked by the participant relative to the “good trait.” The data used in the analysis will be transcribed and rescaled to a score from 0 to 100 from the raw measurements on the Oral Solution or Suspension Palatability Questionnaire.

3.5. Baseline Variables

Baseline characteristics will be collected according to the SoA as specified in the protocol.

4. ANALYSIS SETS (POPULATIONS FOR ANALYSIS)

Data for all participants will be assessed to determine if participants meet the criteria for inclusion in each analysis population prior to releasing the database and classifications will be documented per standard operating procedures.

For purposes of analysis, the following analysis sets are defined:

Participant Analysis Set	Description
Enrolled/Randomly assigned to study intervention	"Enrolled" means a participant's agreement to participate in a clinical study following completion of the informed consent process and screening. Potential participants who are screened for the purpose of determining eligibility for the study, but do not participate in the study, are not considered enrolled, unless otherwise specified by the protocol. A participant will be considered enrolled if the informed consent is not withdrawn prior to participating in any study activity after screening.
Mass balance analysis set	In Cohort 1, the mass balance population analysis set will be defined by evaluable participants who have received 1 dose of [^{14}C]PF-07220060 and who have completed total radioactivity concentration (urinary and fecal) data and who had no protocol deviations that may have affected the mass balance analysis.

Participant Analysis Set	Description
	Participants who vomit CC hours post oral dosing will not be excluded from this population. Participants who vomit within CC hours post oral dose may be removed from the analysis at the discretion of the pharmacokineticist if the event occurs soon after dosing or the resulting mass balance data is deemed anomalous for any other reason.
PK Concentration	
The PK concentration population for PF-07220060 is defined as all participants dosed with PF-07220060 (in both Cohort 1 and 2), who have at least one PF-07220060 concentration.
 
The PK concentration population for [¹⁴C] is defined as all participants dosed with [¹⁴C]PF-07220060 (in both Cohort 1 and 2), who have at least one [¹⁴C] measurement.
 
The PK concentration population for [¹⁴C]PF-07220060 is defined as all participants dosed with [¹⁴C]PF-07220060 in Cohort 2, who have at least one [¹⁴C]PF-07220060 plasma concentration measurement.

PK Parameter	
The PK parameter population for PF-07220060 is defined as all participants dosed with PF-07220060 (in both Cohort 1 or 2), who have at least one estimated PF-07220060 PK parameter of interest.
 
The PK parameter population for total [¹⁴C] is defined as all participants dosed with [¹⁴C]PF-07220060 (in both Cohort 1 or 2), who have at least one total [¹⁴C] PK parameters of interest.
 
The PK parameter population for [¹⁴C]PF-07220060 is defined as all participants dosed with [¹⁴C]PF-07220060 in Cohort 2, who have at least one [¹⁴C]PF-07220060 PK parameter of interest.

Safety Analysis Set	All participants randomly assigned to study intervention and who take at least 1 dose of study intervention. Participants will be analyzed according to the product they actually received.

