### 9.2. Analysis Sets

For purposes of analysis, the following analysis sets are defined:

Participant Analysis Set	Description
Enrolled/Allocated to study intervention	"Enrolled" means a participant's agreement to participate in a clinical study following completion of the informed consent process and screening. Potential participants who are screened for the purpose of determining eligibility for the study, but do not participate in the study, are not considered enrolled, unless otherwise specified by the protocol. A participant will be considered enrolled if the informed consent is not withdrawn prior to participating in any study activity after screening.
Mass balance analysis set	In Cohort 1, the mass balance population analysis set will be defined by evaluable participants who have received 1 dose of [  C]PF-07220060 and who have completed total radioactivity concentration (urinary and fecal) data and who had no protocol deviations that may have affected the mass balance analysis. Further details what participants will be qualified as evaluable participants will be provided in the SAP, however, it should be noted that vomiting within CC hours post oral dose or significant residual activity in the dosing container does not necessarily preclude participants from being evaluable.
PK Concentration	
The PK concentration population for PF-07220060 is defined as all participants dosed with PF-07220060 (in both Cohort 1 and 2), who have at least one PF-07220060 concentration.
 
The PK concentration population for [C] is defined as all participants dosed with [C]PF-07220060 (in both Cohort 1 and 2), who have at least one [C] measurement.
 
The PK concentration population for [C]PF-07220060 is defined as all participants dosed with [C]PF-07220060 in

Participant Analysis Set	Description
	Cohort 2, who have at least one [  C]PF-07220060 plasma concentration measurement.

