2.2. Study Objectives, Endpoints, and Estimands

The following are the objectives and endpoints in this study. Estimand framework will not be applied to this Phase 1 study in healthy participants.

Objectives	Endpoints
Primary:	Primary:

 To characterize the rate and extent of excretion of total radioactivity following administration of a single oral dose of [¹⁴C]PF-07220060. 	
 Mass Balance: Cumulative recovery (%) of radioactivity in urine and feces (adjusted for vomitus, if any), expressed as a percent of total oral radioactive dose administered (quantification by AMS).

 To characterize the metabolic profile for PF-07220060 and identify the circulating and excreted metabolites of PF-07220060 following administration of a single oral dose of [¹⁴C]PF-07220060. 	
 Metabolic profiling/metabolite identification and determination of relative abundance of [¹⁴C]PF-07220060 and its metabolites in plasma, urine and feces, if possible (Cohort 1).
Secondary:	Secondary:

 To determine the absolute oral bioavailability (F) of PF-07220060 from a single oral dose of PF-07220060 under fasted conditions followed by a single IV microdose of [¹⁴C]PF-07220060. 	
 The ratio of dose-normalized plasma AUC_{inf} of oral PF-07220060 (LCMS) and IV [¹⁴C]PF-07220060 (HPLC-AMS) [Cohort 2 only].

 To determine the fraction of PF-07220060 dose absorbed (F_a) from a single oral dose of [¹⁴C]PF-07220060 under fasted conditions. 	
 F_a calculated from the ratio of total recovered radioactivity [¹⁴C] in urine following single dose administration of [¹⁴C]PF-07220060 orally in Cohort 1 and via IV infusion in Cohort 2 (quantification by AMS).

 To determine the safety and tolerability of PF-07220060, administered as a single oral dose of [¹⁴C]PF-07220060 or a single oral dose of PF-07220060 followed by administration of a single IV dose of [¹⁴C]PF-07220060. 	
 AE monitoring, physical examination, clinical laboratory measurements, vital signs and 12-lead ECGs.
Tertiary/Exploratory:	Tertiary/Exploratory:

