6. ANALYSES AND SUMMARIES

6.1. Primary Endpoints

6.1.1. Mass Balance

Individual participant and median data profiles for total radioactivity will be graphically presented for the cumulative recovery of radioactivity in urine, feces and their combination over time in **Cohort 1 only**. Vomitus, if any, will be collected in full during the \square hours after oral dosing in **Cohort 1** and will be required to be prospectively tested for recovered radioactivity. For emesis that occurs after \square hours up to \square hours post dose, samples will be collected in full and stored for potential reflex testing for recovered radioactivity. These participants will not necessarily be excluded from analysis. The total recovery of radioactivity in urine, feces (and vomitus, if any) and their combination will be listed and summarized for **Cohort 1 only**.

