7. INTERIM ANALYSES

No interim analysis will be conducted for this study. As this is an open-label study, the sponsor may conduct reviews of the data during the course of the study for the purpose of safety assessment, facilitating PK modeling, and/or supporting clinical development.

APPENDICES**Appendix 1. Summary of Analyses**

Endpoint	Population	Data Inclusion and Rules for Handling Intercurrent Events and Missing Data	Analysis Method
Mass balance	Mass Balance Analysis Set	Observed data	Descriptive statistics
Metabolite identification/profiling	PK Concentration Analysis Set	Observed data	Descriptive statistics
Absolute oral bioavailability	PK Parameter Analysis Set	Observed and imputed (Section 5.3.1) data	Mixed effect model
Fraction of dose absorbed	PK Parameter Analysis Set	Observed and imputed (Section 5.3.1) data	Mixed effect model or Hodges-Lehmann point estimate
Safety data	Safety Analysis Set	Observed and imputed (Section 5.3.2) data	Descriptive statistics
PK parameters	PK Parameter Analysis Set	Observed and imputed (Section 5.3.1) data	Descriptive statistics
PK concentrations	PK Concentration Analysis Set	Observed and imputed (Section 5.3.1) data	Descriptive statistics
Taste assessment data	Safety Analysis Set, have at least 1 taste assessment performed	Observed data	Descriptive statistics

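### SAP Section 4 lets a Cohort 1 participant who vomits early be removed from the primary mass balance set because his own recovery looks anomalous

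*SAP*

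**What the plan says.** The primary mass balance endpoint (SAP Section 2.2) is "Cumulative recovery (%) of radioactivity in urine and feces (adjusted for vomitus, if any"), as a percentage of the oral radioactive dose. SAP Appendix 1 assigns it to the "Mass Balance Analysis Set", with observed data and descriptive statistics.

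Protocol Section 9.2 says that early vomiting "does not necessarily preclude participants from being evaluable", and passes the rule on: "Further details what participants will be qualified as evaluable participants will be provided in the SAP".

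SAP Section 4 supplies that rule in two sentences, both with the hours redacted. One group of vomiters is kept: those who vomit a stated number of "hours post oral dosing will not be excluded from this population". Those who vomit within the stated window may be removed "at the discretion of the pharmacokineticist if the event occurs soon after dosing or the resulting mass balance data is deemed anomalous". In full, the second trigger reads "or the resulting mass balance data is deemed anomalous for any other reason".

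SAP Section 4 also says that membership of each set is settled and documented before the database is released. SAP Section 6.1.1 says that vomitus from the first stated period "will be required to be prospectively tested for recovered radioactivity". Later vomitus is stored for possible testing.

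**The concern.** The two triggers are joined by *or*, so the second is enough on its own. It refers to the participant's mass balance result, which is the quantity the analysis set exists to summarize. Inclusion can therefore depend on the primary outcome, at one person's discretion and without a stated criterion. Vomiting within the window only opens the door; after that, any reason for finding the recovery odd will do. A participant with the same recovery who did not vomit is not exposed to this rule.

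At stake is the credibility of the reported recovery (mean, median, SD and range) in a cohort of about 6. If a low result is removed because it is low, the summary looks higher and tighter than the data were. A reader of the report could not judge by how much, since no summary with and without the excluded participant is planned.

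**Working it through.** The plan has no figure to reproduce. Protocol Section 9.5 sets about 6 per cohort by convention, without a precision target, and SAP Section 5.1 states that no hypothesis is tested. The check is a reading of the text, followed by arithmetic on assumed values.

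**1. Is anomalous defined for recovery?** No. SAP Section 5.3.1 defines an anomalous *concentration*: grossly inconsistent with other concentrations, after bioanalytical validity has been verified. Nothing equivalent exists for mass balance, and the first trigger's closeness to dosing is not defined either.

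**2. Can the decision be made with the result in view?** Yes. Protocol Section 4.1 discharges Cohort 1 participants on cumulative recovery of at least 90%, or on less than 1% per 24 hours over 2 consecutive days, or at Day 14. The first two criteria need running individual recovery. The study is open-label, and SAP Section 7 lets the sponsor review data while it runs. Settling the sets before database release does not hide recovery from whoever decides.

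**3. Effect of one exclusion.** Assumed recoveries (not from the documents): 92, 90, 89, 88, 86, 70%.

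| | All 6 | Without the 70% |
|---|---|---|
| Mean | 515/6 = 85.8 | 445/5 = 89.0 |
| SD | √(320.83/5) = 8.0 | √(20/4) = 2.2 |
| Median | (88+89)/2 = 88.5 | 89.0 |

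In general, dropping one of 6 with recovery *r*, when the other five average *m*, shifts the mean by (*m* − *r*)/6. Here that is (89 − 70)/6 = 3.2 points. With five at 90% and the vomiter at 80, 70, 60, 50 or 40%, the shift is 1.7, 3.3, 5.0, 6.7 or 8.3 points.

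**4. Average effect over repeated studies.** Assumptions: recovery is normal with mean 88% and SD 3, 5 or 10; vomiting is unrelated to recovery; there are 1 or 2 early vomiters among 6; each is removed if below 80% or 85%. With 400,000 simulated cohorts per setting, the upward bias in the mean ran from 0.01 to 1.37 points. The largest fall in average SD was from 9.51 to 9.01. For one vomiter and cut-off *c* the bias has a closed form, SD × φ((*c* − 88)/SD)/6, where φ is the standard normal density. With SD 10 and *c* = 80 this is 10 × 0.2897/6 = 0.48, which agrees with the simulation.

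**5. Chance that the rule is reached.** P(at least one early vomiter among 6) = 1 − (1 − *p*)^6. For assumed rates *p* of 2, 5 and 10% this is 11, 27 and 47%.

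**The case against.** The best defense is that some discretion over early vomiters is legitimate. Counting the vomitus restores total recovery only. The objective covers rate and extent of excretion, and SAP Section 3.1.1 reports urine and feces separately by interval as a percentage of administered dose. A participant who vomits unabsorbed drug has distorted urine and fecal fractions even if all vomitus is captured. SAP Section 5.3.1 treats PK parameters in the same spirit: an estimate known to be biased by vomiting is footnoted and left out of the statistics. This stands. A reader might infer that excluding vomiters is never needed because vomitus is collected and counted, and the documents do not support that. Nor do the redacted hours allow the exclusion window to be matched to the mandatory testing window. But the PK rule starts from a known cause of bias, whereas the second trigger here starts from the look of the result.

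The rule is also optional, documented and confined to early vomiters, and the median, which SAP Section 6.1.1 plots, hardly moves in the example. Anomalous could also mean too high. All true, and it limits the size of the point. It does not supply a criterion. If vomitus was lost and the total is low for that reason, the recorded collection failure justifies exclusion without looking at recovery.

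A reader might also infer that an excluded vomiter would be replaced. Protocol Section 4.1 and SAP Section 2.3 allow added participants only for those who withdraw or discontinue treatment *and* are non-evaluable. A participant who vomits after his single dose and completes collection is not clearly covered.

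**Conclusion.** The point holds. As written, SAP Section 4 makes membership of the primary mass balance set depend on the primary outcome for early vomiters, by undefined discretion, when recovery can already be known. This is a stated rule, not a missing detail.

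Its size is modest. One exclusion can move the mean by several points and shrink the SD sharply (85.8 to 89.0 and 8.0 to 2.2 in the example), while the median moves by 0.5. The average bias under the simulated assumptions is about 0 to 1.4 points. Recoveries, SDs, cut-offs and vomiting rates are all assumed. It would go too far to say that the reported recovery will be inflated or that an error rate is affected: nothing is tested, removal is optional, and the rule may never be used. It should still be corrected, because the correction is cheap and the cohort is small enough for one exclusion to show.

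**What to change.** - In SAP Section 4, delete "or the resulting mass balance data is deemed anomalous for any other reason".
- Base any vomiting exclusion on criteria written into the SAP in advance that do not use urine, fecal or total recovery: the recorded time of emesis against a stated cut-off (replacing the undefined closeness to dosing), and documented incomplete collection of vomitus. Radioactivity measured in the vomitus is best left out of the criteria, since it is part of the endpoint. Requiring the decision before recovery is seen may not be workable, because recovery is tracked for discharge; criteria fixed beforehand serve the purpose.
- Report mass balance for all dosed Cohort 1 participants with complete urine and fecal collections, vomitus counted, beside the set without any excluded vomiter, and give the reason for each exclusion.

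The cost is SAP wording and one extra summary column, with no change to dosing, sampling or care. The all-participants summary may include someone whose urine and fecal fractions were distorted by vomiting; a footnote can flag this.

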5. GENERAL METHODOLOGY AND CONVENTIONS

Final analysis will be performed after study participant data set release following last participant last visit.

5.1. Hypotheses and Decision Rules

No statistical hypothesis will be tested in this study.

5.2. General Methods

5.2.1. Analyses for Binary/Categorical Endpoints

For binary or categorical variables, number of participants, numbers and percentages of participants meeting the categorical criteria will be presented in accordance with the Clinical Data Interchange Standards Consortium and Pfizer Standards (CaPS).

5.2.2. Analyses for Continuous Endpoints

For continuous variables, the data will be summarized using the number of participants, mean, median, standard deviation (SD), minimum, and maximum in accordance with the CaPS. For appropriate PK parameters, geometric mean and geometric coefficient of variation (%CV) will also be summarized.

5.3. Methods to Manage Missing Data

5.3.1. Pharmacokinetic Data

Methods to handle missing PK data are described below.

Concentrations Below the Limit of Quantification:

In all data presentations (except listings), concentrations below the limit of quantification (BLQ) will be set to zero. (In listings BLQ values will be reported as “<LLQ”, where LLQ will be replaced with the value for the lower limit of quantification.).

Deviations, Missing Concentrations and Anomalous Values:

In summary tables and plots of median profiles, statistics will be calculated having set concentrations to missing if one of the following cases is true:

1. A concentration has been collected as ND (ie, not done) or NS (ie, no sample).
2. A deviation in sampling time is of sufficient concern or a concentration has been flagged as anomalous by the pharmacokineticist.

Note that summary statistics will not be presented at a particular time point if more than 50% of the data are missing.

An anomalous concentration value is one that, after verification of bioanalytical validity, is grossly inconsistent with other concentration data from the same individual or from other participants. For example, a BLQ concentration that is between quantifiable values from the same dose is considered as anomalous. Anomalous concentration values may be excluded from PK analysis at the discretion of the PK analyst or pharmacokineticist.

PK Parameters:

Actual PK sampling times will be used in the derivation of PK parameters. If a PK parameter cannot be derived from a participant's concentration data, the parameter will be coded as NC (ie, not calculated). (Note that NC values will not be generated beyond the day that a participant discontinues). In summary tables, statistics will be calculated by setting NC values to missing; and statistics will be presented for a particular treatment with ≥ 3 evaluable measurements. PK parameter analyses will not be performed for a particular parameter if more than 50% of the data are NC.

If an individual participant has a known biased estimate of a PK parameter (due for example to an unexpected event such as vomiting before all the compound is adequately absorbed from the gastrointestinal tract), this will be footnoted in summary tables and will not be included in the calculation of summary statistics or statistical analyses.

